8.3.5 Month 1 Visit (\pm 5 days)

Patients will be instructed to not administer morning dose of study treatment the day of a study visit. In addition, patients will be asked to refrain from use of SAT for 1 day prior to each study visit. One day prior to each study visit begins on the morning of the day before the study visit and continues until the end of the study visit.

The following procedures and assessments will be performed during the month 1 visit:

- Concomitant medications. Ensure to query use of:
 - Lid hygiene (ie, warm compress, lid massage, lid scrub)
 - SAT
 - Any artificial tear products other than SAT
 - Oral or topical macrolides, tetracyclines, tetracycline derivative drugs
- Hair evaluation

- Visual acuity
- Biomicroscopy (includes upper and lower lid margin appearance evaluation)
- TBUT
- Sodium fluorescein corneal staining (Oxford scheme)
- Sodium fluorescein conjunctival staining (Oxford scheme)
- At least 10-minute wait
- Schirmer's tear test with anesthesia

- IOP
- Contact IxRS
- Blood and urine sample collection for hematology, blood chemistry, PSA measurement, and urinalysis
- Pre-dose blood sample collection for pharmacokinetic analysis (testosterone, DHT, SHBG) (performed for selected patients); time of the collection should align \pm 1 hour to the pre-dose collection performed at the standardization (day -21) visit.
- In-office administration of study treatment (If patient is not participating in pharmacokinetic blood draws, time of in-office administration should be scheduled to align to the baseline (day 1) administration time of day \pm 1 hour. For all patients participating in blood sampling for pharmacokinetic analysis, study treatment should be administered at approximately the same time of day during each office visit and within 10 min after the time the pre-dose blood sample collection was performed at the current visit)
- Post-dose blood sample collection for systemic pharmacokinetics (5 minutes \pm 1 minute, 10 minutes \pm 1 minute, 30 minutes \pm 5 minutes, 2 hours \pm 15 minutes, 4 hours \pm 30 minutes, 6 hours \pm 30 minutes and 12 hours \pm 30 minutes) (for selected patients)
- Adverse events
- Study treatment dispensing
- SAT dispensing
- Collect unused study treatment

8.3.6 Month 3 Visit (\pm 7 days)

Patients will be instructed to not administer morning dose of study treatment the day of a study visit. In addition, patients will be asked to refrain from use of SAT for 1 day prior to each study visit. One day prior to each study visit begins on the morning of the day before the study visit and continues until the end of the study visit.

The following procedures and assessments will be performed during the month 3 visit:

- Concomitant medications. Ensure to query use of:
 - Lid hygiene (warm compress, lid massage, lid scrub)

- SAT
- Any artificial tear products other than SAT
- Oral or topical macrolides, tetracyclines, tetracycline derivative drugs
- Vital signs (pulse rate, blood pressure)
- Hair evaluation
- [REDACTED]
- [REDACTED]
- [REDACTED]
- Visual acuity
- Biomicroscopy (includes upper and lower lid margin appearance evaluation)
- TBUT
- Sodium fluorescein corneal staining (Oxford scheme)
- Sodium fluorescein conjunctival staining (Oxford scheme)
- At least 10-minute wait
- Schirmer's tear test with anesthesia
- IOP
- Contact IxRS
- Blood and urine sample collection for hematology, blood chemistry, PSA measurement, and urinalysis
- Pre-dose blood sample collection for pharmacokinetic analysis [REDACTED] [REDACTED] (performed for selected patients); time of the collection should align \pm 1 hour to the pre-dose collection performed at the standardization (day -21) visit.
- In-office administration of study treatment (If patient is not participating in pharmacokinetic blood draws, time of in-office administration should be scheduled to align to the baseline (day 1) administration time of day \pm 1 hour. For all patients participating in blood sampling for pharmacokinetic analysis, study treatment should be administered at approximately the same time of day during each office visit and within 10 min after the time the pre-dose blood sample collection was performed at the current visit)

[figure not shown]
- Adverse events
- Study treatment dispensing
- SAT dispensing
- Collect unused study treatment

8.3.7 Month 6 Visit (\pm 7 days)

Patients will be instructed to not administer morning dose of study treatment the day of a study visit. In addition, patients will be asked to refrain from use of SAT for 1 day prior to each study visit. One day prior to each study visit begins on the morning of the day before the study visit and continues until the end of the study visit.

The following procedures and assessments will be performed during the month 6 visit:

- Concomitant medications. Ensure to query use of:
 - Lid hygiene (ie, warm compress, lid massage, lid scrub)
 - SAT
 - Any artificial tear products other than SAT
 - Oral or topical macrolides, tetracyclines, tetracycline derivative drugs
- Vital signs (pulse rate, blood pressure)
- Hair evaluation

- Visual acuity
- Biomicroscopy (includes upper and lower lid margin appearance evaluation)
- TBUT
- Sodium fluorescein corneal staining (Oxford scheme)
- Sodium fluorescein conjunctival staining (Oxford scheme)
- At least 10-minute wait
- Schirmer's tear test with anesthesia

- Lower lid margin meibomian gland secretion evaluation
- IOP
- Ophthalmoscopy
- Contact IxRS
- Blood and urine sample collection for hematology, blood chemistry, PSA measurement, and urinalysis
- Pre-dose blood sample collection for pharmacokinetic analysis (testosterone, DHT, SHBG) (performed for selected patients); time of the collection should align \pm 1 hour to the pre-dose collection performed at the standardization (day -21) visit.
- In-office administration of study treatment (If patient is not participating in pharmacokinetic blood draws, time of in-office administration should be scheduled to align to the baseline (day 1) administration time of day \pm 1 hour. For all patients participating in blood sampling for pharmacokinetic analysis, study treatment should be administered at approximately the same time of day during each office visit and within 10 min after the time the pre-dose blood sample collection was performed at the current visit)
- Post-dose blood sample collection for systemic pharmacokinetics (for selected patients); the sample collection should be performed at 10 minutes \pm 1 minute only
- Adverse events
- Study treatment dispensing
- SAT dispensing
- Collect unused study treatment

8.3.8 Month 9 Visit (\pm 14 days)

Patients will be instructed to not administer morning dose of study treatment the day of a study visit. In addition, patients will be asked to refrain from use of SAT for 1 day prior to each study visit. One day prior to each study visit begins on the morning of the day before the study visit and continues until the end of the study visit.

The following procedures and assessments will be performed during the month 9 visit:

- Medication history/concomitant medications. Ensure to query use of:

- Lid hygiene (warm compress, lid massage, lid scrub)
- SAT
- Any artificial tear products other than SAT
- Oral or topical macrolides, tetracyclines, tetracycline derivative drugs
- Vital signs (pulse rate, blood pressure)
- Hair evaluation
- [REDACTED]
- [REDACTED]
- [REDACTED]
- Visual acuity
- Biomicroscopy (includes upper and lower lid margin appearance evaluation)
- TBUT
- Sodium fluorescein corneal staining (Oxford scheme)
- Sodium fluorescein conjunctival staining (Oxford scheme)
- At least 10-minute wait
- Schirmer's tear test with anesthesia
- IOP
- Contact IxRS
- Blood and urine sample collection for hematology, blood chemistry, PSA measurement, and urinalysis
- Pre-dose blood sample collection for pharmacokinetic analysis ([REDACTED] [REDACTED]) (performed for selected patients); time of the collection should align \pm 1 hour to the pre-dose collection performed at the standardization (day -21) visit.

[figure not shown]
- In-office administration of study treatment (If patient is not participating in pharmacokinetic blood draws, time of in-office administration should be scheduled to align to the baseline (day 1) administration time of day \pm 1 hour. For all patients participating in blood sampling for pharmacokinetic analysis, study treatment should be administered at approximately the same time of day during each office visit and within 10 min after the time the pre-dose blood sample collection was performed at the current visit)
- Adverse events
- Study treatment dispensing
- SAT dispensing
- Collect unused study treatment

8.3.9 Month 12/Study Exit (Early Exit) (\pm 14 days)

Patients will be instructed to not administer morning dose of study treatment the day of a study visit. In addition, patients will be asked to refrain from use of SAT for 1 day prior to each study visit. One day prior to each study visit begins on the morning of the day before the study visit and continues until the end of the study visit.

Patients who exit early from the study should complete the month 12/study exit visit procedures when possible. The following procedures and assessments will be performed during the month 12/study exit visit:

- Concomitant medications. Ensure to query use of:
 - Lid hygiene (warm compress, lid massage, lid scrub)
 - SAT
 - Any artificial tear products other than SAT
 - Oral or topical macrolides, tetracyclines, tetracycline derivatives
- Vital signs (pulse rate, blood pressure)
- Hair evaluation

- Visual acuity
- Biomicroscopy (includes upper and lower lid margin appearance evaluation)
- TBUT
- Sodium fluorescein corneal staining (Oxford scheme)
- Sodium fluorescein conjunctival staining (Oxford scheme)
- At least 10-minute wait
- Schirmer's tear test with anesthesia
- Lower lid margin meibomian gland secretion evaluation
- IOP
- Ophthalmoscopy
- Contact IxRS (only for patients who are exiting early from the study)
- Blood and urine sample collection for hematology, blood chemistry, PSA measurement, and urinalysis
- Blood sample collection for pharmacokinetic analysis [REDACTED] (performed for selected patients); time of the collection should align \pm 1 hour to the pre-dose collection performed at the standardization (day -21) visit.
- Adverse events
- Collect unused study treatment

8.4 Instructions for the Patients

- Non-PK patients: Return to the study site for study visits at days -21, -14, 1 and months 1, 3, 6, 9, and 12. Visits should be scheduled so that in-office administration of study treatment at months 1, 3, 6, 9, and 12 will be \pm 1 hour from the time of day established at baseline (day 1).
- PK patients: Return to the study site for study visits at days -21, -14, 1, and months 1, 3, 6, 9, and 12. Visits should be scheduled so that the time of the pre-dose blood sample collection in the morning will be at approximately the same time of day during each office visit (\pm 1 hour from the pre-dose blood sample collection time at the standardization (day -21) visit).

- Patients should remain at the site for the duration of the visit to complete the study-related procedures as explained to them by the study site personnel.
- If glasses are worn for vision correction, patients should remember to bring their glasses each time they visit the doctor's office.
- Follow the study visit schedule and to report all changes in their medical condition to the site.
- Maintain a stable dose if any concomitant medication is taken.
- Report any changes to their medication at their next study visit or report any new medication(s) initiated during the study. Patients should also be reminded to contact the study site if they are experiencing any difficulties during their study participation.

DOSING INFORMATION

- Directions will be provided on proper dosing technique and storage of study treatment. For study treatment dosing, patients will be instructed that each vial from their kit is for single-use dosing; 1 drop should be instilled in each eye from the first vial for the morning dose and a second (new) vial should be used to instill one-drop in each eye for the evening dose.
- If SAT is required for intolerable symptoms, any use of SAT should be instilled at least 30 minutes before or 30 minutes after study treatment whenever both medications are used.
- Patients are NOT to administer SAT or study treatment on the morning of study days -14, -1 and months 1, 3, 6, 9, and 12, as the first (morning) dose on these days will be administered by site staff.
- To administer 1 drop of SAT in each eye on the evening of study day -21 and 1 drop of study treatment in each eye on the evening of study days -14 and 1 and months 1, 3, 6, and 9.
- Save all unused study treatment vials in their study treatment kit and to bring their study treatment kit(s) with them on day 1 and months 1, 3, 6, 9 and 12.
- During the open-label period beginning after the month 6 visit and through month 12/study exit, patients may resume lid hygiene or artificial tears as needed, but use of artificial tears will continue to be prohibited within 24 hours of any study visit.

8.5 Unscheduled Visits

Patients may experience adverse events that necessitate their returning to the study site for unscheduled visits. The adverse event and all required information should be recorded on the appropriate eCRF and the patient's record should include all relevant information.

Unscheduled visits may be performed as necessary to ensure the safety and wellbeing of patients during the study period. Unscheduled visit eCRFs should be completed for each unscheduled visit. An assessment of any adverse event should be completed.

8.6 Compliance with Protocol

Patients must be able to adhere to the study visit schedule, testing parameters, and appropriate inclusion, exclusion, and treatment criteria as described in the protocol.

At each study visit, patients will be asked if they have used any concomitant medications/therapies or had any concurrent procedures since the previous visit.

8.7 Early Discontinuation of Patients

Patients may voluntarily withdraw from the study at any time.

Notification of early patient discontinuation from the study and the reason for discontinuation will be made to the sponsor and will be clearly documented on the appropriate case report form.

8.8 Withdrawal Criteria

Patients may voluntarily withdraw from the study at any time. [Table 6](#) describes the applicable follow-up depending on whether an enrolled study patient decides to discontinue voluntarily, or is discontinued by the investigator or by Allergan.

Table 6 Early Discontinuation Requirements

Reason for Discontinuation	Study Procedures and Visits Requirements
Patient elects to not complete a full study visit	Early exit procedures, as described in Table 1 , should be completed before the end of that visit, whenever possible.
Patient elects to discontinue after completion of enrollment visit and assignment into a study cohort but before exit visit is initiated	No additional procedures or study visits are required.
Patient is discontinued after completion of the enrollment visit due to patient not qualifying for a study cohort or cohort is full (and thus patient is not asked to return for additional study visits)	No additional procedures or study visits are required.
Patient discontinued at the investigator's discretion	Early exit procedures, as described in Table 1, should be completed before the end of that visit, whenever possible.
Patient discontinued at Allergan's discretion	Early exit procedures, as described in Table 1, should be completed before the end of that visit, whenever possible.

Notification of patient's early discontinuation from the study and the reason for discontinuation will be made to Allergan or to the site in the case of patient not qualifying for a cohort or if cohort enrollment goal is met, and will be clearly documented on the eCRF.

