Use of lid hygiene (ie, warm compress, lid massage, lid scrub) or artificial tears (other than the SAT) are prohibited from the standardization (day -21) visit until after the month 6 visit. Starting at the standardization (day -21) visit, all eligible patients will administer SAT twice daily in each eye for 6 days.

From the vehicle run-in (day -14) visit until the month 6 visit, use of SAT will be considered rescue therapy for intolerable symptoms. After the month 6 visit until the month 12/study exit visit, use of lid hygiene and/or any artificial tear product(s) will be unrestricted except for the use of artificial tears 24 hours prior to any study visit. The morning dose of SAT (day -21 only) or study treatment will be administered by site staff on days when there is a study visit. All other doses will be administered by the patient.

All procedures are described in [Table 1](#) and study design is diagrammed in [Figure 1](#).

Randomization/Stratification: Patients will be randomized to receive 0.1% AGN-195263, or its vehicle in a 1:1 ratio. The randomization will be stratified by gender and by baseline (day 1) overall ocular discomfort score (1 vs 2 to 3).

Visit Schedule: Up to 9 scheduled visits: screening (day -51), standardization (day -21), vehicle run-in (day -14), baseline (randomization, day 1), months 1, 3, 6 (primary and secondary efficacy assessment), 9, and 12/study exit (safety assessment). For patients who discontinue the study early, the month 12/study exit visit procedures should be completed when possible.

For patients not participating in the collection of blood samples for pharmacokinetic analysis: in-office study treatment should be administered in the morning at approximately the same time of day during each office visit (\pm 1 hour from the study administration time at baseline [day 1]). At any time, the morning dose should not exceed 1:00 pm local time.

For patients who participate in the collection of blood samples for pharmacokinetic analysis:

- 1) the time of the pre-dose blood sample collection should be scheduled in the morning at approximately the same time of day during each office visit (\pm 1 hour from the pre-dose blood sample collection time at the standardization [day -21] visit).
- 2) SAT or study treatment should be administered in the morning at approximately the same time of day during each office visit and within 10 min after the time the pre-dose blood sample collection was performed that day.

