5.5 Method for Assignment to Treatment Groups/Randomization

Prior to initiation of screening procedures, each patient will provide informed consent. At the standardization (day -21) visit the site will call the interactive voice response system (IVRS) or log onto the interactive web response system (IWRS) to obtain the patient number that will serve as the patient identification number on all study documents.

An automated interactive (telephone or web) response system (IxRS) will be used to manage the run-in and randomization study treatment assignment based on randomization schemes prepared by Allergan Biostatistics. Study medication, including the run-in vehicle, will be labeled with medication kit numbers and shipped to each site.

At the time of enrollment at the vehicle run-in visit (day -14), all eligible patients will be assigned vehicle. At the patient's vehicle run-in visit, the IxRS system will provide the site with the specific medication kit number(s) to use for each qualified patient.

At the time of the baseline visit (randomization, day 1), patients meeting the inclusion/exclusion criteria ([Sections 4.3](#) and [4.4](#)) will be placed into 1 of 4 stratification groups as described in [Section 5.4](#). Eligible patients will be randomly assigned to receive either 0.1% AGN-195263 [REDACTED] or its vehicle in a 1:1 treatment allocation. Based on the randomization scheme, a randomization number associated with 1 of the 2 treatment arms will be assigned to each patient sequentially according to the order of enrollment within the patient's stratification group. That is, IxRS will assign the next available randomization number for the stratification group to the patient at the time the investigator requests randomization. IVRS/IWRS will report a medication kit number to use for each patient corresponding to the randomization number.

The site will dispense the study medication kit assigned by the IxRS according to the IVRS/IWRS instructions. Sites will also call the IVRS or log onto the IWRS at all subsequent visits to obtain a study medication kit number for dispensing study medication. Sites will receive the IxRS confirmation notifications for each transaction. All notifications are to be maintained with the study source documents.

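### Table 6 asks less of sites when a randomized patient chooses to leave between visits than the Protocol Summary and Section 8.3.9 do, so exit safety examinations may not be sought

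*Combined protocol and SAP*

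**What the plan says.** Two places state a general rule. The Protocol Summary, under Visit Schedule, says: "For patients who discontinue the study early, the month 12/study exit visit procedures should be completed when possible". Section 8.3.9 repeats it: "Patients who exit early from the study should complete the month 12/study exit visit procedures when possible". Neither makes an exception for voluntary withdrawal, and the Section 8.3.9 list has a step meant for these patients alone: "Contact IxRS (only for patients who are exiting early from the study".

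Section 8.8 then introduces Table 6 as the table that "describes the applicable follow-up depending on whether an enrolled study patient decides to discontinue voluntarily" or is withdrawn by the investigator or the sponsor. Its rows differ:

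- Rows 1, 4 and 5 (patient does not finish a visit; investigator's decision; sponsor's decision) ask for early exit procedures whenever possible, by the end of the visit in question.
- Row 2 covers "Patient elects to discontinue after completion of enrollment visit and assignment into a study cohort but before exit visit is initiated". Its requirement is "No additional procedures or study visits are required".
- Row 3 gives the same requirement for a patient who does not qualify for a cohort or finds the cohort full.

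The sentence after the table says that notification goes to the sponsor "or to the site in the case of patient not qualifying for a cohort or if cohort enrollment goal is met".

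**The concern.** Row 1 already deals with a patient who stops partway through a visit. Row 2 is therefore most naturally read as the patient who withdraws between visits, although it does not use those words. Section 8.2 sets the enrollment visit at day 1, so row 2 reaches patients who have been randomized and treated. For them, the table that sites would consult on discontinuation is weaker than the general rule.

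Safety over 12 months is one of the two clinical hypotheses (Section 2.2). Ophthalmoscopy, vital signs, laboratory tests, PSA and hair evaluation are listed safety measures (Section 6.3), and several of them are scheduled sparsely. If the exit visit is not sought, some treated patients will have no on-study value for them. The cohort wording adds to the doubt about whom the rows cover, because Sections 3 and 5.4 describe two randomized arms and define no cohorts.

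**Working it through.** **1. The instructions side by side**

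| Source | Who | What is asked |
|---|---|---|
| Protocol Summary, Visit Schedule | all who discontinue early | exit procedures when possible |
| Section 8.3.9 | all who exit early | exit procedures when possible |
| Table 6, rows 1, 4, 5 | patient stops during a visit; investigator or sponsor decision | exit procedures whenever possible, by the end of that visit |
| Table 6, row 2 | patient elects to leave after enrollment visit and assignment, before an exit visit starts | nothing further required |

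No row of Table 6 asks a site to arrange an exit visit for someone who leaves between visits.

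**2. Which examinations depend on the exit visit** (visit lists in Sections 8.3.2 and 8.3.4 to 8.3.9)

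| Examination | Day -21 | Day 1 | M1 | M3 | M6 | M9 | M12/exit |
|---|---|---|---|---|---|---|---|
| Ophthalmoscopy | yes | yes | no | no | yes | no | yes |
| Vital signs | yes | yes | no | yes | yes | yes | yes |
| Laboratory tests, PSA | yes | no | yes | yes | yes | yes | yes |
| Hair evaluation | yes | yes | yes | yes | yes | yes | yes |

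At month 6, ophthalmoscopy is listed before the in-office dose, and Section 8.3 recommends following the listed order. A former vehicle patient's month 6 examination therefore precedes the first dose of active drug.

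**3. Longest time on treatment without the examination if no exit visit is made** (visit windows of 5 to 14 days not added)

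- Ophthalmoscopy, leaving before month 6: 6 - 0 = 6 months.
- Ophthalmoscopy after starting active drug, former vehicle patients leaving after month 6: 12 - 6 = 6 months.
- Vital signs, leaving before month 3: 3 - 0 = 3 months.
- Laboratory tests, PSA and hair evaluation, leaving before month 1: 1 - 0 = 1 month after day 1.

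**4. How many patients**

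The plan's figure is reproduced first. Section 7.6 gives 20.0% versus 9.8%, 85% power and two-sided 0.05, using a pooled z-test with continuity correction. With d = 0.102 and mean rate 0.149:

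- Without correction: n0 = [1.960 × √(2 × 0.149 × 0.851) + 1.036 × √(0.20 × 0.80 + 0.098 × 0.902)]² / 0.102² = 217.3, that is 218.
- With correction: n = (n0/4) × [1 + √(1 + 4/(n0 × d))]² = 236.5, that is 237 per arm, as stated.
- Total: 2 × 237 = 474, and 474/0.90 = 526.7, planned as 527.

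Leavers before month 6 under the 10% assumption: 527 - 474 = 53 (53/527 = 10.1%). This counts every reason for leaving. Those affected are the subset who leave voluntarily, between visits, and would have attended if asked, so the range is 0 to about 53. After month 6, about 237 vehicle patients would switch to active drug under the same assumption. The plan states no attrition for that phase, so no count can be given.

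**The case against.** The best defence is that the texts are compatible. Not requiring a visit and asking for it when possible can both be true. Row 2 can be read as respecting the right to withdraw, and a site reading everything would invite the patient without insisting. This stands in part. A reader might infer a flat contradiction, or that exit visits are forbidden; neither is supported. What remains is a weaker instruction in the table presented as the applicable follow-up. The right to withdraw does not explain the difference, because row 1 also concerns a patient's own choice and still asks for exit procedures.

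A reader might also infer that adverse events after the last attended visit are lost. The documents do not support that:

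- Section 8.4 tells patients to report changes in their condition and to contact the site about difficulties.
- Section 8.5 provides unscheduled visits.
- Section 8.7 requires the reason for leaving to be documented.
- Section 9.1.1 requires all reported events to be recorded.
- Section 9.3 keeps serious events reportable for at least 28 days after the last dose, with follow-up.

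Only the routine visit-based question goes unasked.

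Another tempting reading is that the start of row 2 is undefined, because Section 5.5 says "At the time of enrollment at the vehicle run-in visit (day -14), all eligible patients will be assigned vehicle". That is a loose use of the word. Row 2 refers to the enrollment visit, and Section 8.2 uses that term for day 1.

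Other limits are fair. Visual acuity, biomicroscopy and IOP are also done at months 1, 3 and 9. Completers too go six months between ophthalmoscopies. An exit examination may come after dosing has stopped. Table 1 is not visible in the public copy, so an early exit column or footnote there could not be checked.

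**Conclusion.** The point holds as a minor but worthwhile correction. For a randomized patient who chooses to leave between visits, Table 6 does not ask for the exit procedures that the Protocol Summary and Section 8.3.9 request. At worst, this leaves up to about 6 months of treatment without ophthalmoscopy, about 3 months without vital signs, and about 1 month without laboratory tests, PSA or hair evaluation.

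The conclusion assumes that row 2 means withdrawal between visits, that assignment there means randomization, and that the Section 8.3 lists match Table 1. The number of patients is unknown; the bound of 53 applies only before month 6 and only under the planned 10% attrition.

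A reader might infer bias in the primary result through the last-observation rule in Section 7.3. The documents do not support that. They give neither the number of such leavers nor their split by arm, so no direction or size can be attached, and no such effect is claimed.

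**What to change.** Amend Table 6 and the sentence that follows it:

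- **Row 2:** apply it to a randomized patient who elects to discontinue between visits. Ask for the Section 8.3.9 exit procedures when possible and with the patient's agreement.
- **Row 3:** apply it to a patient who is not randomized, whether through not qualifying or through withdrawing before randomization, including during the vehicle run-in. Keep "No additional procedures or study visits are required". Voluntary leavers during the run-in then have a row of their own.
- **Rows 4 and 5:** replace the limit to the end of the current visit with: at that visit or, if between visits, at an exit visit.
- **Cohort wording:** delete it from rows 2 and 3, and delete "or to the site in the case of patient not qualifying for a cohort or if cohort enrollment goal is met" from the closing sentence.

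The cost is a few lines in an amendment, since Section 8.3.9 already specifies the procedures. Sites would have a few more exit visits to arrange, which patients may decline.
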